**1.I.b. Control Intervention – Supportive Therapy**

Although we considered an inactive control condition, such as a wait-list group, we opted for a more scientifically rigorous design for 3 reasons. First, use of an active control condition (ACC), will allow us to test the efficacy of the ‘active’ ingredients of EASE (i.e., mindfulness, emotion awareness, ER strategies). Second, with the inactive control, we would not be able to rule out the effect of factors such as the therapeutic relationship and familial expectation of treatment benefit. Third, use of the active comparator allows for a more rigorous test of effect via independent, assignment-naïve (‘blinded’) evaluators. The ACC will involve non-directive, supportive psychotherapy and education, which is a well-established ACC, often used in RCTs involving youth (e.g., Piacentini et al., 2010) and in trials evaluating MBIs (e.g., Shallcross et al., 2015). We structured the ACC based on guidelines set forth by clinical trial methodologists (e.g., Baskin et al., 2003; Kazdin et al., 1990). The ACC is *structurally equivalent* to the experimental intervention in that it is implemented by the same therapists, over 16 50- to 60- minute sessions, in an individual format. Additionally, the purported *active ingredients* of EASE are expressly contraindicated in the ACC. In the ACC, the clients and parents will be allowed to discuss any topics and stressors with the therapist, but the therapist is prohibited from providing mindfulness training.

**1.I.c. Overview.** We propose to conduct a sufficiently powered RCT of EASE, across two clinical sites. The design and participant flow is depicted in Figure 6.

**1.I.d. Sample and Ascertainment**

Sample. A sample of n = 80 male and female adolescents and young adults with ASD will be enrolled. The expected male to female ratio is 4:1, based on current prevalence estimates of diagnosed ASD. With a conservative estimate of 25% attrition, we would achieve a final sample size of 60. Pitt will enroll 50 participants, and VT will enroll 30 (due to budget restrictions and population access).

**Figure 6.** RCT Design

Inclusion criteria consist of: (1) an ASD diagnosis, based on expert clinical opinion and supported by ADOS-2; (2) age 14-21 years; (3) Verbal IQ  $\geq$  80; (4) fluency in English; (5) a parent available and willing to participate; (6) evidence of at least an average degree of ER impairment for ASD (T-score of 45 or higher or 0.5 SD below the mean; on the Emotion Dysregulation Inventory Reactivity Short Form); and (7) medications are permitted but must be stable for 4 weeks with no planned changes.

Exclusion criteria consist of: (1) Current suicidality or homicidality that warrants more immediate care; (2) active psychosis; (3) Receiving concurrent psychotherapy treatment for emotional issues (i.e., depression, anxiety, anger) that overlaps with the current study.

Recruitment. This study will take place at: The University of Pittsburgh (Pitt.) in Pittsburgh, PA and Virginia Tech (VT) in Blacksburg, VA. Pitt Sample. [name] is associated with the Center for Excellence in Autism Research which has been running studies with verbal individuals with ASD for 30+ years. [name] recently completed two studies with adolescents (10-17 and 12-19) with ASD. In an assessment-focused study, 30 adolescents were recruited within less than 2 years. In an fMRI study, 26 adolescents with ASD were enrolled within 1 year. [name] also leads a study on the ASD specialized psychiatric inpatient unit at Western Psychiatric Institute and Clinic, where the reason for admission is typically emotional and behavioral dysregulation; this will be an ongoing source of recruitment (upon discharge). Finally, [name] has established collaborations and recruitment strategies in place with the Pittsburgh Autism Treatment Network and a high-volume outpatient clinical for ASD. VT Sample. In a recently completed RCT with adolescents with ASD, over a 24-month recruitment period, 36 potential participants were screened for eligibility (which was more stringent than current study), of whom 83% ( $n = 30$ ) met study criteria and were randomized. In two separate funded treatment trials currently underway, [name] is enrolling (on average) 2 adolescents and 2 adults per month. The clinic where this study will take place is well-recognized in the community, with a waiting list for treatment and registries carried over from prior studies. Additionally, [name] is a stakeholder and affiliate of the VT Center for Autism Research, a large-scale participant registry of children and adults with ASD interested in treatment research.

Eligibility determination and sample characterization will begin by phone, following verbal consent to screen. Phone screening will include a brief interview about the inclusion and exclusion criteria, including the 7-item EDI Reactivity Short Form. If participants pass the phone screen, they will complete an in-person informed consent/assent and assessment to confirm their ASD diagnosis and ensure that their Verbal IQ  $\geq$  80.

Randomization. Participants will be randomly assigned to EASE or ACC once eligibility is confirmed, by a data manager independent from the PIs and clinical team. Randomization algorithms have been created by the study statistician, independent of the PIs. Randomization will be done to ensure equal numbers of EASE and ACC at each site. Group assignment will be communicated to the PIs and assigned study clinician, who will then inform the participant. Site PI's ([name] and [name]) will closely monitor screening and randomization procedures and, should difficulties (e.g., more withdrawals from ACC than active) arise, they will be addressed immediately with the Data Safety and Monitoring Board.

Therapist training: At the start of the RCT, all therapists will convene for a training meeting for both treatments, on site at Pitt. The PIs will provide the theoretical background and didactic training, including live and video (from open pilot) demonstration of specific strategies. Study therapists must observe each recorded session (from open trial) before delivering that session with a study participant. In addition, every session of the first case of every therapist will be observed for integrity and training purposes by the respective site PI.

'Blind' maintenance: All Independent Evaluators will be 'blind,' or naive, to treatment assignment, and they will instruct participants not to reveal what intervention that they are receiving during the course of the procedures. Meetings with the independent raters will be conducted in a different office than the therapy, and the therapists and PI's will not be involved in outcome assessment. Regular assessments of treatment naive status will be conducted by the PI. When questions arise about possible need to break the blind (e.g., a potentially serious event becomes apparent during an assessment, but evaluator is not aware of treatment condition), [name] (Co-I at Pitt) will be the first contact. She will work with the PI's to determine how to proceed. If a participant breaks the blind, we will get another rater.

## 1.1.e. Study Variables and Measurement

A multi-method, multi-informant assessment battery (see Table 2) will be used to provide accurate sample characterization and examine change. All measures have well-established psychometric properties for the full age range of our sample and have been used with ASD samples. We are employing **four primary reporters**: self, parent, other (e.g., teacher, co-worker), and assignment-blind clinical rater, and **four modalities of assessment**: direct testing, observational, questionnaire, and interview. Assessments will be completed at pre-treatment (baseline), midpoint (8 weeks), post-treatment (16 weeks), and follow-up (3 months after post-treatment), in addition to the primary measure of ER completed weekly by parents.

### Characterization:

ASD and IQ inclusion criteria will be confirmed by: (1) the Autism Diagnostic Observation Schedule – Second Edition (ADOS-2), a semi-structured, standardized assessment that elicits behaviors relevant to the diagnosis of ASD administered by a research reliable ADOS tester (Lord et al. 2012), and (2) the Wechsler Abbreviated Scale of Intelligence, Second Edition (WASI-2; Wechsler et al., 2011), a reliable and valid measure of intelligence based on four subtests provide a brief, general estimate of functioning and a verbal IQ.

Measures with well-established psychometrics in ASD will be administered to quantify characteristics that may be related to ER and treatment response, including: (1): A subset from the Delis-Kaplan Executive Function System (D-KEFS; Delis et al., 2001) executive functioning battery including the Sorting task, which assesses conceptual reasoning and problem-solving, and the Color-Word Interference task, which assesses inhibitory control; (2) The 12-item Intolerance of Uncertainty Scale (IUS-12) which measures inhibitory and prospective anxiety (Boulter et al., 2014; Maisel et al., 2016); (3) The Social Responsiveness Scale, 2nd Edition (SRS-2) as a measure of ASD symptom severity, including specific subscales designed to assess treatment effects (Constantino et al., 2004; Constantino & Gruber, 2012); and (4) a well-validated and non-invasive self-report measure of puberty, the Pubertal Development Scale (PDS; Carskadon & Acebo, 1993).

Prior to treatment, caregivers and participants with ASD will separately complete a Needs Assessment, which was developed specifically for EASE to inform case conceptualization. It is a 19-item questionnaire that asked the rater to provide ratings of difficulty, on a 1-10 scale, for situations related to ER and socialization, as well as qualitative descriptions for any relevant items.

Information on Medications and Other Treatments will collected at each time point by parent report. We gather medication data by medication class. The parent report form also gathers information about non-pharmacological treatments (e.g., social skills training) by answering yes or not to a common list of interventions as well as an option to add open-ended additional information. Information is gathered on any changes in the past 4 weeks for all medications and psychosocial interventions endorsed.

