#### **1.K.a. Potential Challenges, Alternative Strategies, and Design Considerations**

*What if EASE does not work?* Although our preliminary data suggest that EASE will have a positive impact, it is possible that this RCT with a larger sample will not yield consistent results. Even if there is not evidence for the efficacy of EASE, results will inform our understanding, and treatment, of ER-related problems in ASD. It is possible, for instance, that mindfulness improves but not ER in measurable ways. It is also conceivable that ER moves but that this change is not reflected in symptomatic improvement. This study is designed such that, even if unsuccessful, the results will inform subsequent treatment research in this area.

*How will we handle use of other treatments?* EASE takes about 16 weeks to complete from start to finish (plus the 3-month follow-up). Based on our pilot studies and prior clinical work, we anticipate most participants will be involved in other treatments. We will not enroll participants who are actively engaged in treatment that targets ER; however, treatments such as speech therapy and family counseling will be permitted. Pharmacological treatment is permitted as well. Given prior research and the sample in our pilot study, we anticipate the majority of this sample will be medicated, and medication changes (e.g., altered dosages) are common, even though inclusion requires medication to be consistent at enrollment without planned changes. We will collect data on other treatments and changes in medication so that we can subsequently determine if this is associated with response.

*Why a high-functioning sample?* We deliberated on the minimum level of cognitive and verbal ability necessary for participation in this treatment, and have determined that the program is likely to be most accessible to people who do not have co-occurring intellectual disability (ID) and are verbally communicative; as such we have restricted eligibility with regard to verbal ability. Additionally, there are unique risks faced by people without ID during transition to adulthood (Taylor & Mailick, 2014), and emotional problems and high negative affect are most pronounced among higher functioning adolescents with ASD, compared to lower functioning peers (e.g., Sukhodolsky et al., 2008).

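### The medication-change question looks back 4 weeks, but post-baseline assessments are 8, 8 and about 13 weeks apart, so dose changes and transient treatments in about 17 of 29 weeks are not captured

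*Combined protocol and SAP*

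**What the plan says.** Section 1.1.e sets the schedule: "Assessments will be completed at pre-treatment (baseline), midpoint (8 weeks), post-treatment (16 weeks), and follow-up (3 months after post-treatment"). The only measure it describes as collected more often is the weekly parent rating of emotion regulation.

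The Characterization part of that section describes the form:

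- Timing: "Information on Medications and Other Treatments will collected at each time point by parent report".
- Drugs: "We gather medication data by medication class".
- Non-drug treatment: parents report by "answering yes or not to a common list of interventions as well as an option to add open-ended additional information".
- Changes: "Information is gathered on any changes in the past 4 weeks for all medications and psychosocial interventions endorsed".

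Section 1.K.a, on use of other treatments, expects most of the sample to be medicated and says that "medication changes (e.g., altered dosages) are common, even though inclusion requires medication to be consistent at enrollment without planned changes". It then gives the purpose of the data: "We will collect data on other treatments and changes in medication so that we can subsequently determine if this is associated with response".

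In section 1.J.a, the paragraph on medication effects promises to compare medication usage between groups and to adjust if needed. The Aim 1 analysis puts medication information into every mixed model as a covariate. Neither place says whether that means baseline use, current class or change.

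**The concern.** A 4-week look-back suits the entry rule in section 1.I.d, which requires 4 weeks of stable medication. The same look-back is then used at visits 8 to 13 weeks after the previous one, and no reason is given for that. No section describes a medication log between assessments.

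The gap matters because of the kind of change the plan expects. Its own example of a common change is an altered dosage, and a dosage change leaves the medication class as it was. Comparing one form with the next cannot reveal it; only the change question can. A participant whose dose was altered in week 2 or week 10 would, on the form as described, look the same as one with no change. The check in section 1.K.a would then relate response to a change variable that misclassifies some participants.

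**Working it through.** The documents give no coverage figure, so there is none to reproduce.

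**Inputs**

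- Look-back: 4 weeks (1.1.e, Characterization).
- Assessments: weeks 0, 8 and 16, and 3 months after week 16 (1.1.e). Three months is taken as 13 weeks, so follow-up is at about week 29.

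**Uncovered time.** For each interval, uncovered weeks = max(0, interval − 4).

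| Interval | Length (weeks) | Covered | Uncovered | Weeks in no window |
|---|---|---|---|---|
| Baseline to midpoint | 8 | 4 | 4 | 1–4 |
| Midpoint to post-treatment | 8 | 4 | 4 | 9–12 |
| Post-treatment to follow-up | 13 | 4 | 9 | 17–25 |
| Total | 29 | 12 | 17 | |

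- Overall: 17/29 = 58.6% uncovered, 12/29 = 41.4% covered.
- Treatment period: (4 + 4)/16 = 50% uncovered.
- Follow-up: 9/13 = 69.2% uncovered.

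**Sensitivity to the length of 3 months**

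| Follow-up interval | Overall uncovered | Follow-up uncovered |
|---|---|---|
| 12 weeks | 16/28 = 57.1% | 8/12 = 66.7% |
| 13 weeks | 17/29 = 58.6% | 9/13 = 69.2% |
| 14 weeks | 18/30 = 60.0% | 10/14 = 71.4% |

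**Which changes the uncovered time applies to**

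| Change in an uncovered week | Seen by comparing forms? |
|---|---|
| Class or listed intervention started or stopped, and still so at the next form | Yes, but undated |
| Dose change | No |
| Swap within a class | No |
| Treatment begun and ended before the next window opens | No, unless the parent volunteers it in the open field for non-drug treatments |

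**From time to changes.** The share of time equals the share of missed dose, within-class and transient changes only if these are spread evenly over the 29 weeks. The documents give no rate. Entry requires that no change be planned, so fewer changes in the first weeks is plausible. As an extreme illustration, suppose none occur in weeks 1–4 and the rest are spread evenly over weeks 5–29. The share missed is then 4/12 = 33% during treatment and (17 − 4)/(29 − 4) = 13/25 = 52% overall.

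**The case against.** **The form asks about more than recent changes.** It records medication class and a yes/no list of interventions at every time point. A reader might infer that 59% of post-baseline time is simply unobserved. The documents do not support that, because a lasting change of class or intervention shows up at the next form with only its date missing. This objection stands, and it limits the point to dose changes, within-class swaps and transient treatments.

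**Damage to the efficacy analyses is not shown.** A reader might infer that the medication adjustment and the Aim 3 durability analysis rest on misclassified data. The Aim 1 covariate is not defined as change, and class-level use at each visit could supply it. The Aim 3 plan does not mention medication changes, and the documents state no rule on treatment changes during follow-up. The intent-to-treat comparison needs none of these data. This also stands.

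**The form itself is not in the documents.** It might record drug name or dose under each class. The text describes only class-level recording, and the markings in Table 2 cannot be read in the available copy. The point therefore concerns the form as described.

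**Four weeks has merits.** It limits recall error and covers the period just before each rating. That is fair, but it does not answer the gap: a change that is never asked about cannot be recalled at all, and a 4-week flag can be kept alongside a longer question.

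**Conclusion.** The point holds in limited form. The change question covers 12 of about 29 post-baseline weeks and leaves 17 (about 59%; 57–60% if 3 months is 12–14 weeks) uncovered. That is 50% of the treatment period and about 69% of follow-up. In those weeks, dose changes, within-class swaps and transient treatments are not captured on the form as described, and altered dosage is the plan's own example of a common change.

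The figure should not be read as the share of medication changes missed. It has that meaning only for these types of change, and only if they are spread evenly over time.

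The analysis clearly affected is the section 1.K.a check of whether changes in medication and other treatments are associated with response. The medication covariate in section 1.J.a is affected only if it is defined by change. The randomized comparison stands without these data. This is an inexpensive improvement to a supporting analysis, not a threat to the trial's main result.

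**What to change.** Keep the 4-week question at eligibility and baseline, where it matches the entry rule. At midpoint, post-treatment and follow-up, ask about changes since the last study assessment. Record the approximate date and the type of each change: start, stop, dose increase or dose decrease. Word the question so that treatments already stopped by the visit are included. Keep a flag for changes in the past 4 weeks if the team wants it.

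Define the change variable for the section 1.K.a check from these full-interval data. State in section 1.J.a whether the medication covariate means baseline use, current class or change.

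With intervals of 8, 8 and about 13 weeks fully covered, uncovered time falls from 17 of 29 weeks to none. The cost is a wording change to an existing parent form, with no added visit, and somewhat less accurate parent recall over 8–13 weeks than over 4.

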### Primary Outcome (Emotion Regulation) Measures:

We have two measures of our primary outcome: (1) The EDI, which measures impaired ER, collected weekly parent report (short form), other reporter at pre-, post- and follow-up, and blind rater interview of the participant at pre-, post- and follow-up; and (2) The RSQ self- and parent report as a measure of ER strategies, collected at pre-, mid- and post-treatment, and 3-month follow-up.

Emotion Dysregulation Inventory (EDI; [name] et al., 2016). The EDI was developed to assess the full range of ER impairment observed in ASD. The item pool was created with feedback from parents of youth and young adults with ASD and input from a panel of experts in measure development and ER in ASD. Next, caregivers of 1,755 youth with ASD completed 66 candidate EDI items, and the final 30 were selected based on factor analysis and item response theory (IRT) analyses. The EDI has two scales: 1) *Reactivity*, characterized by intense, rapidly escalating, sustained and poorly regulated negative emotional reactions, and 2) *Dysphoria*, characterized by minimal positive affect and motivation, and the presence of nervousness and sadness. A 7-item Reactivity short form was developed via simulated computerized adaptive testing, which is correlated .98 with the full scale. Validity evidence was supported by expected group differences (higher scores in an ASD

psychiatric inpatient versus community sample), expected correlations with measures of related constructs, and demonstration of change sensitivity. Co-calibration with legacy measures demonstrated that the EDI provides substantially more information on individual variability in ER; Figure 7 shows these test information curves for the full EDI Reactivity scale, the 7-item EDI short form, the ABC-I (15 items), an emotion dysregulation index from the CBCL (Sampson et al., 2014), and CBCL Stress Problems Scale. In a sample of 432 youth with ASD with stable treatments, paired samples t-tests across a 4-week period yielded a very small effect size (-0.06), which will be helpful in judging the meaning of EDI effect sizes for EASE.

**Response to Stress Questionnaire, Social Stress Version** (RSQ; Connor-Smith et al., 2000) is a 57-item self- and parent-report questionnaire of ER strategies. The RSQ asks the respondent to identify social stressors that they have experienced and then rate the questions related to these specific stressors, thereby making it more concrete and relevant to the lives of adolescents young adults with ASD. The RSQ has been shown to be valid and reliable in ASD samples ([name] et al., 2014; Khor et al., 2014). The RSQ will be used to explore the change in reliance upon maladaptive strategies (i.e., involuntary engagement and involuntary disengagement).

### Secondary Outcome Measures.

[figure not shown]
**Functional/Adaptive Outcome Measures:** Our secondary functional outcome measures include: (1) The CGI, and (2) the CAFAS, both completed by a blind rater at pre- and post-treatment, and follow-up.

**Clinical Global Impression** (CGI; Guy, 1976). The CGI is comprised of 2 scales: Severity (CGI-S) and Improvement (CGI-I), each rated on a 7-point scale. The CGI-I scale was designed to measure overall symptomatic change as compared to baseline. Scores range from 1 (Very Much Improved) to 4 (Unchanged) to 7 (Very Much Worse). The CGI-I has been used in many studies over the past 3 decades, including clinical trials of treatments for ASD (e.g., RUPP, 2002). In this study, the CGI-I is used as a categorical (responder vs. non-responder) outcome measure, and will assess global functioning (including functioning in school, activities of daily living, social activities, and home). In our open trial to pilot EASE, we successfully trained three independent raters to reliably assign CGI scores and established inter-rater agreement as well, cross-site.

**Child and Adolescent Functional Assessment** (CAFAS; Hodges, 2000). The CAFAS evaluates level of impairment in day-to-day functioning. It has over 20 years of research to support its sensitivity to change and has been applied in child welfare, juvenile justice, mental health, and school systems to identify level of functioning and needs. CAFAS domains include: School, Home, Community, Behavior Towards Others, Moods/emotions, Self Harm, Substance Use, and Thinking (assessing irrational thinking). The CAFAS has been widely used, including with samples that involved children with ASD (e.g., Bishop-Fitzpatrick et al., 2015).

**Psychiatric Symptoms/Problem Behavior:** Our primary measure of psychiatric symptoms and problem behavior will be the BPRS completed by a blind rater at pre, post-, and follow-up time points. In addition, we have several parent, self, and other reporter questionnaires of specific symptoms and problem behaviors that will be completed to allow tests of convergence across multiple reporters as well as to provide the possibility to evaluate composites via structural equation modeling, depending on the primary results.

**Brief Psychiatric Rating Scale, Version 4.0** (BPRS; Ventura et al., 1993). The BPRS is an interview-based measure of psychopathology severity that has been widely used in clinical trials administered by treatment naive raters (e.g., Zanello et al., 2013). It has been previously used in an RCT of Cognitive Enhancement Therapy for ASD and was responsive to change (Eack et al., 2013). It has 24 items assessing

**Figure 7.** Test information comparison of EDI to other measures

severity of psychiatric symptoms on a scale from 1 (not present) to 7 (extremely severe) that are rated after administration of structured probes.

Aberrant Behavior Checklist (ABC; Aman et al., 1985). The ABC is a 59-item questionnaire with 5 subscales: Irritability (ABC-I), Social withdrawal (ABC-S), Stereotypic behavior, Hyperactivity/noncompliance, and Inappropriate Speech. ABC-I measures tantrums, aggression, and self-injury, and has been utilized in ASD treatment and medication studies (Aman, 2012). However, a confirmatory factor analysis of the ABC found the highest corresponding items for the Irritability subscale were self-injury and aggression items rather than items referencing tantrums (Kaat et al., 2014). Thus, the proposed study will use the ABC-I as a measure of problem behaviors more broadly. In a recent review of 38 measures of social communication concluded that the ABC-S, an index of social interaction and isolation, has the most data to support its use in clinical trials in ASD as a change-sensitive measure of social functioning (Anagnostou et al., 2015).

Measures of psychiatric symptoms will include: (1) The PROMIS Anxiety and Depression Scales (Irwin et al., 2010), which were developed via the NIH Patient-Reported Outcomes Measurement Information Systems (PROMIS) initiative as brief change-sensitive outcome measures; they were responsive to change in our open trial; (2). Five complementary forms from the Achenbach System of Empirically Based Assessment (ASEBA; Achenbach & Rescorla, 2001), including the: ABCL: other/parent-report on adult; ASR: adult self-report; CBCL: parent-report; YSR: self-report; TRF: other/teacher report). The ASEBA forms are co-normed, allowing us to examine convergence and discrepancy across reporters. The ASEBA yield t-scores for internalizing and externalizing behavior problems, as well as a range of syndrome scales (e.g., aggression, depression). The ASEBA has been widely used, including in ASD samples (e.g., Stratis & Lecavalier, 2017).

